Discuss the research design including but not limited to such issues as: probability of group assignment, potential for subject to be randomized to placebo group, use of control subjects, etc.

This is a cluster randomized trial. We assessed 12 cluster sites for potential eligibility and excluded 4 sites (around Malawi) because they could not provide reliable delivery data. Of the 8 cluster sites chosen, 4 will be randomly allocated to oral health education and xylitol gum and 4 will be allocated to oral health education and no xylitol gum. The randomization will occur as follows: 1. The first site will be randomized, then computer matched by number of deliveries to the non-intervention site. 2. This process will be repeated in sequence until all 8 sites (4 matched sets) are allocated.

Inclusion Criteria:

The following represent our a priori decided upon inclusion criteria: (1) Enrollment at less than or equal to 20 weeks gestation by best obstetrical estimate; or (2) Enrollment post partum with an anticipated next pregnancy within 18 months; or (3) Enrollment preconception with an anticipated pregnancy within 18 months; and (4) Cognitively aware enough to participate in the study; (5) Greater than or equal to 18 years of age (in Malawi, constitutes a legal adult and capacity to consent for study); (6) Willing to participate in the study; (7) Willing to undergo at least two periodontal exams; (8) Willing to chew 1 piece of xylitol gum for 10 minutes after the morning and evening meal (intervention sites); (9) Anticipating to remain within the region for 18 months.

Exclusion Criteria:

(1) Greater than 20 weeks gestation by best obstetrical estimate; (2) Post partum and not anticipating another pregnancy within 18 months; (3) Preconception and not anticipating another pregnancy within 18 months; (4) Not cognitively aware enough to

participate in the study; (5) Not willing to undergo at least two periodontal exams; (6) Less than 18 years of age; (7) Not willing to chew 1 piece of xylitol gum for 10 minutes after the morning and evening meal (intervention sites); (8) Anticipating a move outside of the region within 18 months.

F2. Procedure

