1. Subjects will be recruited by study personnel for potential enrollment during their prenatal visits 2. If enrolled, subjects will be: A) giving medical history/information; B) undergoing a minimum of 2 periodontal exams; (Visit 1 and 2) C) participating in antenatal care; D) chewing xylitol gum (at intervention cluster sites) twice a day following meals; E) undergo delivery (Visit 3) Participants will also be asked to consent to collection of data and potential use of xylitol gum. As previously described, since this product is commercially available over the counter and for the indication of the prevention of dental disease, no IND is necessitated.

Plans for study oversight are as follows: 1. Post-approval, this study will be monitored by the PI and co-PI at BCM in Houston by ensuring that data entry is up to date on a weekly basis. The PI and co-PI will also take regular trips to Malawi to ensure that all study related material is collected and stored according to plan and in compliance with confidentiality requirements. 2. Complaints about the study will be handled by local investigators in Malawi under the guidance of the PI and co-PI at Baylor. 3. Non-compliance on the part of study staff will be addressed by the PI and co-PI. Study staff will be re-educated on study procedures and confidentiality requirements if indicated, and disciplinary action will be taken if appropriate. 4. Unanticipated Problems Involving Risk to Subjects or Others will be handled by local investigators with immediate notification of BCM PIs and co-PIs. Specifically, if there are unanticipated risks or adverse events, then a significant adverse event report will be filed with the Baylor Institutional Review Board and it will also be reported to the Malawi Ministry of Health for evaluation.

Section G: Sample Size/Data Analysis

G1. Sample Size

How many subjects (or specimens, or charts) will be used in this study?

Local: 10360 Worldwide: 10360

Please indicate why you chose the sample size proposed:

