Successful engagement in meaningful global research, and notably a randomized trial, necessitates tremendous up-front leg work and demonstration of feasibility. We have invested three years in preparation for the proposed PPax trial and are confident in having now parsed down the necessary components suggesting that we can execute the proposed trial on budget and on time, that we should execute the proposed study testing xylitol gum as an intervention, and that it will take a cluster randomization design enrolling a total sample size of 9360 subjects at 8 proposed sites to demonstrate effect size.

We have estimated that a total sample size of 9360 subjects will be sufficient to demonstrate a 33% reduction in the primary outcomes of (1) preterm birth <37 and <34 weeks, and (2) associated neonatal morbidity and mortality based upon our prior work in Malawi. In our study design (where the health center serves as the unit of randomization), we have accounted for a 30% loss to follow up and calculated our per site enrollment to necessitate 1170 subjects at each of 8 sites.

G2. Data Analysis

Provide a description of your plan for data analysis. State the types of comparisons you plan (e.g. comparison of means, comparison of proportions, regressions, analysis of variance). Which is the PRIMARY comparison/analysis? How will the analyses proposed relate to the primary purposes of your study?

Intercluster (between cluster) analysis will include univariate and multivariate analyses analyzing the number of clusters, average cluster size, range of cluster size, rate of preterm birth, rate of neonatal complications, rate of periodontal disease, rate of maternal comorbidities, range and variance of each measure; analysis by intention to treat and by multivariate measures with GEE. Intracluster (per subject, by cluster) analysis will include univariate and multivariate analyses analyzing the number of subjects, average gestational age, rate of preterm birth, rate of neonatal complications, rate of periodontal disease, rate of maternal comorbidities, range and variance of each measure; analysis by intention to treat and by multivariate measures with GEE.

Section H: Potential Risks/Discomforts

H1. Potential Risks/Discomforts

Describe and assess any potential risks/discomforts; (physical, psychological, social, legal, or other) and assess the likelihood and seriousness of such risks:

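### Sites are randomised before they are matched, one at a time: on the literal wording the odds of xylitol depend on delivery volume, and with sites taken in random order the pairs are never better, and usually worse, than if formed first

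*Combined protocol and SAP*

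**What the plan says.** Section F1 (Design) of the combined protocol and SAP describes a cluster randomised trial with eight sites: "Of the 8 cluster sites chosen, 4 will be randomly allocated to oral health education and xylitol gum", and the other four are controls. The allocation has two steps. The first is: "The first site will be randomized, then computer matched by number of deliveries to the non-intervention site". The second is: "This process will be repeated in sequence until all 8 sites (4 matched sets) are allocated". G1 confirms the unit ("where the health center serves as the unit of randomization") and plans equal enrolment ("calculated our per site enrollment to necessitate 1170 subjects at each of 8 sites").

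So randomisation comes before matching, one pair at a time, and number of deliveries is the only matching variable. Three things are not stated:

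- whether being randomised means being drawn to receive xylitol or being given a coin flip for arm;
- the order in which sites are taken;
- the rule by which the computer finds a match.

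The F1 prompt asks about the probability of group assignment. The answer gives four sites against four, but no probability per site. No delivery counts appear anywhere. The analysis plan in G2 names intention to treat and GEE, and mentions neither the pairs nor adjustment for delivery volume.

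**The concern.** The usual order in a matched-pair cluster trial is to form the pairs and then toss a fair coin within each. Here the order is reversed, with two possible consequences.

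First, the match is called the non-intervention site, which suggests that the drawn site takes xylitol and its nearest remaining neighbour becomes the control. A site with unusually many or few deliveries is seldom another site's nearest neighbour, so it seldom enters as a control. It tends to receive xylitol because it is drawn.

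Second, even if the drawn site's arm is decided by a coin, taking sites in random order and matching each to its nearest remaining neighbour can use up a good partner early and leave distant sites to be paired at the end.

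With four sites per arm, the allocation mechanism carries much of the weight of the comparison. The sponsor chose delivery volume as the factor to balance, and G2 states nothing that would correct a tilt in it.

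**Working it through.** **The plan's own figures.** Eight sites in four sets give four per arm, and 8 × 1170 = 9360 agrees with the total in the G1 justification. The plan gives no allocation probability and no measure of pair quality to reproduce.

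**Inputs.** From F1: 8 sites, 4 pairs, matching on number of deliveries, randomise then match, in sequence. Assumed, because the plan is silent: the delivery counts; sites drawn in random order; the match is the nearest remaining site, with ties split equally.

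**Far outlier, literal reading.** A site far from all the rest is nobody's nearest neighbour until only two sites remain. It is a control only if it is never drawn. The draws are from 8, 6, 4 and 2 remaining sites:

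P(never drawn) = (7/8)(5/6)(3/4)(1/2) = 0.273, so P(xylitol) = 1 − 0.273 = 0.727.

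This needs no particular volumes, only that one site lies far from the others.

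**General volumes, literal reading.** Let S be the remaining sites and m(d) the nearest remaining neighbour of drawn site d. For site i:

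p_i(S) = (1/|S|) × [1 + sum of p_i(S without d and m(d)) over draws d where neither d nor m(d) is i].

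The expected total pair gap follows the same recursion:

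g(S) = (1/|S|) × sum over d of [|x_d − x_m(d)| + g(S without d and m(d))].

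Dividing by 4 gives the mean gap per pair. The gap is the same whether the drawn site gets xylitol or a coin flip.

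**Pairing first.** Sort the sites and pair adjacent ones. Even spacing: (200 + 200 + 200 + 200)/4 = 200. Outlier: (100 + 100 + 100 + 2600)/4 = 725.

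**Results on assumed volumes (exact recursion).**

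| Assumed deliveries per site | P(xylitol), literal reading | Expected mean deliveries, xylitol v control, literal reading | Mean pair gap, sequential v pairs first |
|---|---|---|---|
| 600 to 2000 in steps of 200 | ends 0.603; their neighbours 0.415; others 0.471 to 0.511 | 1300 v 1300 | 298 v 200 |
| 800 to 1400 in steps of 100, plus 4000 | outlier 0.727; others 0.400 to 0.603 | 1613 v 1312 | 794 v 725 |
| 500, 750, 1125, 1690, 2530, 3800, 5700, 8540 | 0.367 to 0.690 | 3383 v 2775 | 1770 v 1231 |
| 1000, 1050, 2000, 2080, 3000, 3110, 4000, 4150 | 0.500 for every site | equal | 97.5 v 97.5 |

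The relative excess in pair gap is 298/200 − 1 = 49% with even spacing, 794/725 − 1 = 10% with the outlier, 1770/1231 − 1 = 44% in the third pattern, and nil with clear natural pairs.

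**Random volumes.** Over 400 random sets from each of three distributions (two lognormal, one uniform), the mean total within-pair difference was 20% to 27% larger than with pairs formed first. Sequential matching was equal in 2.5% to 6.25% of sets and better in none. On the literal reading the largest site averaged 0.60 to 0.66.

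**Where the effects vanish.** With a coin flip for the drawn site, P(xylitol) is 0.50 for every site. When sites were processed in size order, the pairs were identical to pairing first in 10,000 of 10,000 sets.

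**The case against.** The strongest reply is that the sentence is terse rather than faulty. To randomise a site ordinarily means to assign it to an arm by chance, and the preceding sentence says the intervention sites are randomly allocated. On that reading every site has probability 1/2. Nor does F1 say that sites are taken in random order or that the match is to the nearest remaining site. If the computer works in size order or matches globally, the pairs are as good as they can be. All of this stands. A reader might infer that the procedure gives poorer pairs under any reading; that is not so.

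The size is also uncertain. The 0.73 and the arm difference of 1613 against 1312 need a site far from the rest. With even spacing the odds are unequal, but the arms balance on deliveries in expectation. In the outlier pattern one arm must take the large site whatever is done: the mean absolute arm difference in deliveries is 698 on the literal reading and 650 with pairs first, about 7% better. This too stands.

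Finally, a reader might infer that the xylitol arm would be weighted towards referral or urban sites, or that power is lost. The documents do not support either. Section J2 describes an urban-rural region but links no site's volume to its setting. Nothing shows that deliveries predict preterm birth, and equal enrolment of 1170 per site is planned. No effect on type I error, power or the treatment estimate has been calculated here.

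The reply does not defend the wording itself. The phrase about the non-intervention site does point to the literal reading, and nothing elsewhere in the plan rules it out.

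**Conclusion.** The point holds as a weakness in the stated allocation procedure, not as proof that the allocation is biased. On the literal reading, a site's chance of xylitol depends on its delivery volume: 0.73 for a far outlier, and about 0.60 for end sites and 0.41 for their neighbours when volumes are evenly spaced. On the coin-flip reading the odds are fair, but with sites taken in random order sequential nearest matching never beats pairing first and usually does worse. In the assumed patterns the excess in mean pair gap runs from nil (clear natural pairs) through 10% (one outlier) to 49% (even spacing).

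These sizes rest on assumed delivery counts, random draw order and nearest-neighbour matching, none of which the plan states. The 0.73 needs no specific counts, but it does need the literal reading, random order and one site far from the rest. What is certain is that F1 as written does not establish equal odds or a reproducible allocation, and that a standard procedure would do so whichever reading was meant.

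**What to change.** Replace the two allocation steps in F1 with the following:

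1. Rank the eight sites by number of deliveries over a stated reference period.
2. Form all four pairs from adjacent ranks before any allocation.
3. Randomise within each pair with probability 1/2, using one documented seed.
4. State that every site has allocation probability 1/2.

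This makes the odds equal and gives the smallest total within-pair difference in deliveries, whichever reading was intended. The cost is one rewritten paragraph: the sites, the matching variable and the sample size stay as they are.

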The potential risks to participants in this study are minor and include the physical risks associated with some of the sample and data collection, risk of psychological distress, and risks to privacy. a. Physical Risks: Intervention: there are no known significant risks to chewing gum. b. Psychological Risks: There is no recognized potential risk of psychological distress to the study participants as a result of reflecting on their diagnosis and health history. c. Privacy Risks: There is a small, potential risk of loss of confidentiality. Stringent methods described below will be employed to protect against this risk such that this risk is unlikely.

H2. Data and safety monitoring plan

Do the study activities impart greater than minimal risk to subjects?

No

H3. Coordination of information among sites for multi-site research

Is the BCM Principal Investigator acting as the SPONSOR-INVESTIGATOR for this multi-site research?

Yes

Is BCM the COORDINATING CENTER for this multi-site research?

Yes

If the answer to EITHER of the questions above is "Yes", please complete the following questions:

If this is a multicenter study and the BCM PI is an INVESTIGATOR with responsibilities of SPONSOR or if BCM is the COORDINATING CENTER, describe the management of information among the sites related to participant protections. Your description should include reporting of unanticipated problems, protocol modifications, IRB and/or institutional approvals, and interim results among the sites.

We will follow rigorous procedures to ensure the accuracy, quality, and confidentiality of study data. These procedures include staff training and retraining, close supervision, a Manual of Procedures, and quality control reviews.

[name] is a PhD trained bioinformatician with a background in anthropology. He has worked in [name] laboratory since 2008, and designed and implemented the on-line database utilized in the seed grant. He will continue to execute the database and assure quality data with inset custom QA QC measures. He will additionally coordinate the database entry and personnel, and complete the biostatistical analyses on rolling data.

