Women will be recruited in one of two settings: when they present for prenatal care/ at the time of antenatal booking at less than 20 weeks, or postpartum (on the postpartum ward) or preconception with a desire to have another pregnancy in less than 18 months. Women will be approached by trained and experienced community health workers.

Are foreign language consent forms required for this protocol?

Yes

Which of the following ways will you document informed consent in languages other than English?

A full-length informed consent document

J3. Privacy and Intrusiveness

Will the research involve observation or intrusion in situations where the subjects would normally have an expectation of privacy?

No

J4. Children

Will children be enrolled in the research?

No

J5. Neonates

Will non-viable neonates or neonates of uncertain viability be involved in research?

No

J6. Consent Capacity - Adults who lack capacity

Will Adult subjects who lack the capacity to give informed consent be enrolled in the research?

No

J7. Prisoners

Will Prisoners be enrolled in the research?

No

Section K: Research Related Health Information and Confidentiality

Will research data include identifiable subject information?

Yes

Information from health records such as diagnoses, progress notes, medications, lab or radiology findings, etc.

Yes

Specific information concerning alcohol abuse:

No

Specific information concerning drug abuse:

No

Specific information concerning sickle cell anemia:

No

Specific information concerning HIV:

Yes

Specific information concerning psychiatry notes:

No

Demographic information (name, D.O.B., age, gender, race, etc.):

Yes

Full Social Security #:

No

Partial Social Security # (Last four digits):

No

Billing or financial records:

No

Photographs, videotapes, and/or audiotapes of you:

No

Identifiable biospecimens

No

Other:

No

At what institution will the physical research data be kept?

The physical data is maintained at one of two locations. It is either held securely at the BIPAI Baylor Center of Excellence in Lilongwe, Malawi or in the laboratory of [name] at Baylor College of Medicine, Houston Texas (at study completion).

How will such physical research data be secured?

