As described in our protocol, data will be under secure storage and locked in the secured records room at the BIPAI Baylor COE or in the laboratory of [name]. The enrollment logs are kept separate from the data to reduce risk of identifying information being with deidentified (subject codes).

At what institution will the electronic research data be kept?

Baylor College of Medicine. Data is uploaded in a completely deidentified manner on a secure server and maintained at Baylor College of Medicine.

Such electronic research data will be secured via BCM IT Services- provided secured network storage of electronic research data (Non-Portable devices only):

Yes

Such electronic research data will be secured via Other:

No

Will there be anyone besides the PI, the study staff, the IRB and the sponsor, who will have access to identifiable research data?

No

Please describe the methods of transmission of any research data (including PHI, sensitive, and non-sensitive data) to sponsors and/or collaborators.

If sent to collaborators, it is only sent with SSL encryption.

Will you obtain a Certificate of Confidentiality for this study?

No

Please further discuss any potential confidentiality issues related to this study.

There are no further potential confidentiality issues.

Section L: Cost/Payment

Delineate clinical procedures from research procedures. Will subject's insurance (or subject) be responsible for research related costs? If so state for which items subject's insurance (or subject) will be responsible (surgery, device, drugs, etc). If appropriate, discuss the availability of financial counseling.

Subjects will not be charged to participate. There are no ensuant costs to the research. Costs of the xylitol gum are covered by the Thrasher Research Fund and will not be incurred to the subjects.

If subjects will be paid (money, gift certificates, coupons, etc.) to participate in this research project, please note the total dollar amount (or dollar value amount) and distribution plan (one payment, pro-rated payment, paid upon completion, etc) of the payment.

Dollar Amount:

0

Distribution Plan:

Subjects will not be paid to participate in this research project.

Section M: Genetics

How would you classify your genetic study?

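### Willingness to chew gum is an entry rule at intervention sites only, which creates a partly avoidable risk of selection bias of unknown direction and size

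*Combined protocol and SAP*

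**What the plan says.** Section F1 allocates 8 health centers, 4 to oral health education plus gum and 4 to education without gum. Inclusion (8) reads "Willing to chew 1 piece of xylitol gum for 10 minutes after the morning and evening meal (intervention sites", and exclusion (7) reads "Not willing to chew 1 piece of xylitol gum for 10 minutes after the morning and evening meal (intervention sites". Both are limited to the gum sites. Inclusion (6), general willingness to take part, applies at every site.

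Section F2, item D, describes "chewing xylitol gum (at intervention cluster sites) twice a day following meals". Shortly afterwards, with no limit by site, the section says: "Participants will also be asked to consent to collection of data and potential use of xylitol gum". Section Q lists one English consent form, which is not available for review.

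Women are recruited individually. Section J2 says: "Women will be approached by trained and experienced community health workers". Section O1 says that the study is not placebo-controlled.

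For analysis, section G2 plans "analysis by intention to treat and by multivariate measures with GEE" and names no adjustment set. On records, section K says: "The enrollment logs are kept separate from the data to reduce risk of identifying information". Section H3 says: "These procedures include staff training and retraining, close supervision, a Manual of Procedures, and quality control reviews". Neither says that women excluded under this rule, or women who decline, are recorded.

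**The concern.** Randomizing health centers balances, in expectation, the women who attend them. It does not balance a filter that is applied after allocation and in one arm only. A rule that holds only at gum sites can be used only by staff who know the site's arm, so selection takes place with allocation known.

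If women unwilling to chew differ from willing women in their risk of preterm birth or periodontal disease, the enrolled arms differ before any gum is chewed. The difference could favor the gum, count against it, or be trivial. Enrolling more women does not shrink it.

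Intention to treat protects the comparison among enrolled women, and women screened out at gum sites are never enrolled. Their counterparts at control sites are enrolled, so the result is a baseline imbalance. Covariate-adjusted GEE can reduce that imbalance only as far as measured baseline data explain the link between willingness and risk. Section F2 collects a medical history and a periodontal exam at Visit 1, which could serve, but the plan does not commit to adjusting for either.

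**Working it through.** The protocol has no figure of its own to reproduce here. It gives neither the share of women unwilling to chew nor their risk, so both are assumed below.

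**Apparent effect when the gum does nothing**

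Let u be the share of otherwise eligible women who are unwilling, and r their risk relative to willing women. Gum sites enroll willing women only; control sites enroll both. The apparent risk ratio (gum v control) is

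RR = 1 / (1 − u + u·r),

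whatever the baseline risk.

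| u | r | Calculation | RR |
|---|---|---|---|
| 10% | 1.5 | 1 / 1.05 | 0.952 |
| 20% | 1.5 | 1 / 1.10 | 0.909 |
| 20% | 0.75 | 1 / 0.95 | 1.053 |
| 2% | 0.75 | 1 / 0.995 | 1.005 |
| 2% | 2 | 1 / 1.02 | 0.980 |
| any | 1 | 1 / 1 | 1.000 |

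Section G1 targets a 33% reduction. Against that, 0.952 is (1 − 0.952)/0.33, about 14% of the target, and 0.909 is (1 − 0.909)/0.33, about 28%.

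These values are the total selection on willingness. If every unwilling woman at a gum site would decline under inclusion (6) anyway, criteria (8) and (7) add nothing to it. If none would, they account for all of it. The documents do not say where between these the truth lies.

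**Effect of a matching filter at control sites**

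Suppose that a question at control sites removes a share f of the unwilling women there. The unwilling share among enrolled controls becomes u′ = u(1 − f) / (1 − u·f), and RR = 1 / (1 − u′ + u′·r).

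- f = 0: the values above are unchanged.
- f = 0.5, u = 10%: u′ = 0.05/0.95 = 0.0526, so RR is 0.974 at r = 1.5.
- f = 0.5, u = 20%: u′ = 0.10/0.90 = 0.1111, so RR is 0.947 at r = 1.5 and 1.029 at r = 0.75.
- f = 1: RR is 1.000 in every case.

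**Extra screening at control sites**

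With N control women to enroll, and all unwilling women screened out, the extra number to screen is N/(1 − u) − N. Section G1 gives two totals: 9360 (1170 at each of 8 sites, so N = 4 × 1170 = 4680) and 10360 (N = 5180 if split equally).

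| u | N = 4680 | N = 5180 |
|---|---|---|
| 2% | 96 | 106 |
| 10% | 520 (130 per site) | 576 |
| 20% | 1,170 | 1,295 |

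**The case against.** The strongest objection is about attribution. At a gum site, taking part includes chewing gum, so many women unwilling to chew would probably decline under inclusion (6). Knowledge of the arm at recruitment comes with an open cluster trial that has no placebo, and rewording a criterion does not change that. This stands. It is why the risk is only partly avoidable, and why the risk ratios above cannot be charged to criteria (8) and (7) alone.

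A related objection is that a willingness question at a control site is hypothetical. A yes that costs nothing may screen out few women, leaving f near zero. This also stands, as a limit on the remedy. An alternative is to drop the criterion and keep women who do not chew as non-adherers under intention to treat. That needs no extra screening and does not narrow the population, but selection through inclusion (6) would remain.

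A third objection is that baseline data offer some protection. Medical history and Visit 1 periodontal status can be adjusted for, and comparing them by arm would give indirect evidence of differential selection. This stands in part. No adjustment set is named, and section F2 does not state that the Visit 1 exam precedes gum use. With 4 sites per arm, ordinary differences between sites would also blur the comparison.

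A fourth objection is that the consent sentence in section F2 may already put the gum question to women at all sites. It may, or it may simply mean use that depends on allocation, in which case F1 and F2 agree. It is not an eligibility rule and does not cancel the limit in F1. The consent form and the Manual of Procedures might settle common wording and the recording of refusals. As they are not in view, their absence here is not counted as a defect.

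Finally, refusal may be rare. Section H1 reports no known significant risks from chewing gum, and the documents give no reason to expect 10% or 20% to refuse. At 2% the range is 0.980 to 1.005.

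**Conclusion.** The written eligibility rules differ by arm and are applied with allocation known. That creates a partly avoidable risk of selection bias of unknown direction and size, possibly negligible. The illustrative ratios of 0.91 to 1.05 rest wholly on assumed refusal rates and assumed relative risks, and they describe total selection on willingness. The point is worth acting on because the written asymmetry is cheap to remove, and women screened out without a record cannot be recovered at analysis.

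A reader might infer more than this in three ways:

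- **That the trial will be biased in favor of the gum.** The documents give no refusal rate and no risk for refusers, so neither the existence nor the direction of a bias is shown.
- **That no analysis could help.** The planned GEE, if adjusted for measured baseline covariates, could remove part of the imbalance.
- **That rewording the criteria would remove the problem.** Selection through inclusion (6) would remain, and control-site answers would be hypothetical.

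**What to change.** - Delete the limit to intervention sites from inclusion (8) and exclusion (7). Put one identically worded willingness question to women at all 8 sites, where feasible before the site's arm is discussed.
- Align the consent sentence in section F2, and the consent form, with that criterion, and say whether refusing gum bars entry at a control site.
- Record by site the women approached, those ineligible with the reason, and those declining. The enrollment logs could hold this, or a screening log set out in the Manual of Procedures.
- Compare baseline history and Visit 1 periodontal status by arm, and name in section G2 any covariates used for adjustment.
- State the limitation: this removes the written asymmetry but not all selection in an open cluster trial, and the control-site question may screen out few women.

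The cost is a wording amendment, log entries, and the extra control screening tabulated above, which is small if refusal is rare. Results would apply to women willing to chew gum, as they already do at the gum sites.
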